3.3.3. End-points

Primary End-point:

1. Progression Free Survival (PFS) for patients with ad/mRCC receiving SU.

PFS is defined as: the time from when the patient receives the first dose of SU to the time of progression or death due to any cause, which occurs first.

2. Time to Treatment Failure (TTF) for SU 1st line.

TTF is defined as: from when the patient receives the first dose of SU to the time of SU discontinuation (date completed by the physician).

Secondary End-point:

1. Objective Response Rate (OOR) for adv/mRCC patients receiving SU as 1st line treatment.

ORR is defined as the percentage of patients with confirmed CR or confirmed PR according to RECIST criteria v1.1.

2. Description of SU real life usage of doses across all centers, including description of treatment schedules (dose change, dose schedule, average dose received during the period treatment).

3. Combined PFS for patients with ad/mRCC receiving the 2nd line sequence SU- different treatment.

Combined PFS is defined as: the time from when the patients receives the first dose of SU as first line, until progression or death due to any cause while on the 2nd line treatment, whichever occurs first during the 2nd line sequence treatment.

4. Combined TTF for the SU-2nd line sequence.

Combined TTF is defined: as the time from when the patient receives the first dose with SU as first line, to the time of 2nd line sequence discontinuation (date completed by the physician).

5. OS for adv/mRCC patients receiving SU as first line followed by 2nd line as measured from date of first SU dose to the date of death of any cause. The OS median and the overall survival at month 24 (24 months OS) will be measured.
6. If possible, efficacy parameters (PFS, OS) for the combined 1st line SU- 2nd line sequences according to the second line post SU (other than SU-AXI):
 - SU in 1st line-Axitinib TKI in 2nd line.
 - SU in 1st line- other TKI in 2nd line (sorafenib, pazopanib).
 - SU in 1st line/mTOR in 2nd line (temsirolimus, everolimus).
7. Safety description with AE listing in patients receiving SU: frequencies of patients experiencing at least one AE will be displayed by body system.
8. QoL using the questionnaire Functional Assessment of Cancer Therapy-Kidney Symptom Index 19 (FKSI-19).

CCI

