6.1. Selection of First-Line Treatment

6.1.1. First-Line Treatment in Patients With Favorable- to Intermediate-Risk Clear Cell mRCC

Currently, Phase III data originating from four randomized trials support the use of three molecules in the first-line setting, ie, Sunitinib,^{5,6} pazopanib,⁷ and bevacizumab, in combination with interferon- α .^{8,9} The criteria for choosing between Sunitinib and pazopanib currently represent the hottest topic of debate. Its importance prompted the design and conduct of the first head-to-head Phase III trial comparing two first-line treatment alternatives for mRCC patients.¹⁰

A head-to-head prospective Phase III trial of Sunitinib and pazopanib [COMPARZ], ClinicalTrials.gov identifier NCT00720941¹⁰ the randomized design rested on the non-inferiority comparative effectiveness of 800 mg once daily continuous dosing of pazopanib relative to 50 mg once daily 4/2 weeks dosing of sunitinib. Although there is no doubt that direct comparison of Sunitinib versus pazopanib represents an effort aimed at providing evidence data in regards to two management alternatives for clear cell mRCC patients, many questions pertaining to study results and their interpretation remain unanswered.

The observation of differences in patterns of care between community and academic practice dovetails with other retrospective reports. Choueiri et al. published a series of 144 RCC patients from two tertiary oncology centers in the US. Patients were treated with Sunitinib, sorafenib, or bevacizumab from 2003 to 2008. Treatment patterns, response rates, and adverse events were described.¹² Similar data were obtained from a retrospective review of 250 patients with mRCC treated at 18 community oncology clinics. Differences in outcomes between these two studies included median duration of first line therapy for both Sunitinib (5.9 months in the community vs. 10.5 months in the academic centers) and sorafenib (5.5 vs. 8.1 months). In addition, patients in the community were more likely to receive lower doses of Sunitinib and sorafenib and were more likely to have dose reductions and interruptions than patient in the academic centers. These differences in practice patterns are an important area of further research and may lead to the understanding of more optimal treatment regimens for patients.¹³

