8.7. Sample Size

Due to the non-existence of a sample size calculation/justification for estimating the median progression free survival in phase IV trials and the exploratory/observatory nature of this study, we opt not to base the sample size on the main objective. However, we will use the secondary objective of estimation of the ORR for adv/mRCC patients receiving SU in the 1st line as the basis of the sample size. With 140 patients we will be able to assess the ORR to within a margin of error of at most $\pm 8\%$ using 95% confidence intervals. This is based on the assumption that the ORR will be less than 37% as per the literature.^{12,25} This sample size is also within the range of sample sizes of other studies investigating SU for first line and where PFS and TTF were estimated.²⁵

The 140 patients will be enrolled at 14 sites in the Middle Eastern & African countries; namely UAE, Qatar, RSA, Egypt, Algeria, Tunisia and Morocco. Each site is expected to enroll an average of 10 patients. This will ensure diverse and possibly representative sample of the Middle East and North Africa region.

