8.9. Data Analysis

Detailed methodology for summary and statistical analyses of data collected in this study will be documented in a Statistical Analysis Plan (SAP), which will be dated, filed and maintained by the sponsor. The SAP may modify the plans outlined in the protocol; any major modifications of primary endpoint definitions or their analyses would be reflected in a protocol amendment.

Demographic and other clinical characteristics of the patients will be summarized using the mean, standard deviation, median, minimum, and maximum values, for numeric variables such as age and duration of follow up and frequency distributions for categorical data such as gender. The median and 95% confidence intervals for the main outcomes PFS and TTF will be estimated using the method of Kaplan-Meier. The ORR for adv/mRCC patients receiving SU in the 1st line will be computed along with its 95% confidence interval using the Clopper-Pearson formula. Cox proportional hazard models may be used to explore the potential influences of baseline characteristics on PFS or TTF. A multiple logistic regression model can be used to assess the effect of prognostic variable on ORR.

Change in other variables such as Quality of life and weight at last visit as compared to the baseline will be assessed using the paired t-test at each visit in addition to computing mean differences along with 95% confidence intervals. Moreover, repeated methods can be used to look for trends over time and adjust for possible confounders.

All AEs occurring during the study will be considered as treatment-emergent, and the frequency of AEs will be summarized. Sub-group analyses of association between efficacy outcomes, safety measurements, and baseline factors will be performed for exploratory reasons as needed.

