7.2. Comparative methods

- For two groups of normal distribution, the means of quantitative variables will be compared using the Student’s t- test if the assumption of homogeneity of variance is verified (the Satterthwaite method will be used if the variances are unequal).
- If more than two groups have to be compared, analysis of variance (ANOVA) will be performed for quantitative variables if normality in each group and homoscedasticity are met. Homogeneity of variances will be tested by Levene's test.
- If the assumptions are not verified, alternative parametric testing such as Mann Whitney Wilcoxon and Kruskal-Wallis tests will be applied.
- The association between two qualitative variables will be assessed with the Pearson’s Chi-square test. When the number of values will be less than 5, groups of categories will be proposed or the Fisher’s exact test will be performed.
- For all tests performed, the significance level will be 5%.

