8.2. Safety and tolerability analyses

- **Role:**
To describe safety and tolerability of patients receiving the SU–other sequence”.
- **Population:**
Study population “SU – other sequence” patients
- **Endpoints:**
- Incidence of adverse events (AEs)
- Discontinuation
- Deaths
- **Statistical methods:**
Descriptive methods
- **Method for handling missing values:**
None-Observed-case analysis

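### Adverse events are planned as crude patient frequencies with no visible allowance for time on sunitinib, so any comparison across baseline groups mixes toxicity with length of exposure

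*Protocol*

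**What the plan says.** Protocol 3.3.3 defines the AE endpoint as a share of patients: "frequencies of patients experiencing at least one AE will be displayed by body system". Protocol 8.9 counts every AE during the study as treatment-emergent and continues: "the frequency of AEs will be summarized. Sub-group analyses of association between efficacy outcomes, safety measurements, and baseline factors will be performed". These subgroup analyses are exploratory and done where needed. The section names no method for them.

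SAP 8.2 gives descriptive methods for safety, and its entry for missing values is "None-Observed-case analysis". The legible AE endpoints, just before SAP 5.4, are incidences by grade, discontinuation for AEs, and treatment duration until such discontinuation. The start of that list is missing from the text.

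SAP 7.2 has a general rule: "The association between two qualitative variables will be assessed with the" Pearson chi-square test, or Fisher's exact test when counts are small, at 5%. SAP section 4 sets 5% for all comparisons without multiplicity adjustment. SAP 7.4 applies Kaplan-Meier, log-rank and Cox methods to PFS, TTF, TSF and OS, but not to AEs.

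Protocol 10.1.1 has investigators record AEs that they judge related to SU. SAP 4.1 restricts the safety population to patients who had an AE after the first SU dose.

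**The concern.** If only SU-related events are recorded, the period at risk is broadly the time on SU. That time is individual: Protocol 8.5.3 continues treatment visits past month 12 until SU is stopped, and time to SU discontinuation is itself a primary endpoint. The protocol's background cites a wide spread in median SU duration between two outside series, "5.9 months in the community vs. 10.5 months in the academic centers" (Protocol 6.1.1).

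A baseline group that stops SU sooner has fewer months in which an SU-related event can appear. When stopping is due to progression or death, this lowers its apparent toxicity. When AEs themselves cause stopping, the direction can reverse. A crude percentage cannot separate the two. The analysis by baseline factor could thus report a factor as linked to toxicity when it only changes time on drug. Patterns of toxicity are a stated outcome of the study, so this matters even without a formal test.

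**Working it through.** **The plan's own figure.** The only computed design figure concerns ORR: "With 140 patients we will be able to assess the ORR to within a margin of error of at most" 8 percentage points, with ORR assumed below 37% (Protocol 8.7). The Wald half-width is 1.96 × √(0.37 × 0.63 / 140) = 0.080, so it reproduces. The documents give no figure for AE comparisons beyond the 5% level.

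**Inputs for the AE check**
- 140 patients (Protocol 8.7). A 70/70 split is assumed, because no subgroup sizes are given.
- Median SU durations of 5.9 and 10.5 months. These are background figures from outside series, used here as an assumed gap between two baseline groups.
- Follow-up capped at 24 months, assumed from the visit schedule in Protocol 8.4.1.
- The same constant monthly AE hazard h in both groups. The documents give none, so it is varied.
- Exponential time on SU, with stopping independent of AEs.
- All enrolled patients as denominator; uncorrected Pearson chi-square at 5%.

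**Formula.** With stopping rate μ = ln 2 / median,

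P(AE) = h/(h + μ) × [1 − exp(−24(h + μ))].

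The stopping rates are μ = 0.693/5.9 = 0.1175 and 0.693/10.5 = 0.0660 per month. For h = 0.10:
- shorter exposure: 0.10/0.2175 × (1 − e^(−5.22)) = 0.457
- longer exposure: 0.10/0.1660 × (1 − e^(−3.98)) = 0.591

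Exact enumeration over the two binomials gives rejection in 36% of studies, although the monthly hazards are equal.

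**By pooled AE incidence (70 v 70, 24-month cap)**

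| Pooled incidence | Shorter v longer exposure | Rejection at 5% |
|---|---|---|
| 5% | 4.0% v 6.0% | 7.8% |
| 10% | 8.1% v 11.9% | 11.7% |
| 20% | 16.4% v 23.6% | 18.8% |
| 30% | 25.0% v 35.0% | 25.7% |
| 50% | 43.4% v 56.6% | 35.4% |
| 60% | 53.4% v 66.6% | 35.7% |
| 80% | 75.5% v 84.5% | 27.2% |
| 90% | 87.5% v 92.5% | 17.0% |

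**Sensitivity**
- Follow-up, at hazards 0.03, 0.05, 0.10 and 0.20: 22%, 28%, 36% and 35% with the 24-month cap; 32%, 37%, 40% and 35% with no cap.
- Smaller exposure gap: at most 20% for 7 v 10.5 months, and at most 11% for 8.1 v 10.5 months.
- Larger exposure gap: up to 78% for 4 v 10.5 months.
- Split of 35/105 or 105/35: at most 30%.
- Early-onset AEs at 5.9 v 10.5 months: 7% to 17% with a front-loaded hazard (Weibull shape 0.5), and 6% to 9% if AEs occur only in the first 3 months.
- Equal time on SU: 5.1% to 5.2%, so the excess comes from the exposure gap.
- The SAP safety set as denominator: 10% to 28%, and 0% for any AE, because every patient in that set has one.

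**After the fix.** Comparing first-AE rates per patient-month gives 4.9% to 5.5% in the constant-hazard, 70/70, 5.9 v 10.5 month scenario. This is under the same model that the rate comparison assumes.

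**The case against.** The strongest reply is that no AE test is planned. SAP 8.2 is descriptive and lists no subgroups, and the AE table shell in SAP 9.5 has a single sunitinib column with no split by baseline factor. SAP 7.2 is a general rule, Protocol 8.9 is exploratory, and Protocol 8.11 calls the study hypothesis-generating. This stands: the chi-square result is conditional on an analyst applying the general rule. It does not remove the problem, because Protocol 8.9 does plan to relate safety to baseline factors and offers nothing that accounts for exposure.

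Second, crude incidence is a valid description of the share of patients affected, which is the stated endpoint. This also stands. A reader might call the excess rejections false positives with no difference in AE risk. In fact only the monthly hazard is equal; the cumulative risk on SU differs.

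Third, a reader might infer that groups stopping early will always look less toxic. The documents do not support that. Protocol 6.1.1 says the shorter-duration community patients had more dose reductions and interruptions, Protocol 6.1.1 also links AEs to treatment alteration in the first months, and the SAP has an endpoint for stopping because of AEs.

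Finally, part of the SAP's AE endpoint section is missing from the text, so an exposure measure there cannot be excluded.

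**Conclusion.** The point holds as a cheap improvement. AEs are planned as crude patient frequencies, the recorded events depend on time on SU, a comparison by baseline factor is foreseen, and no readable section adjusts for exposure. The direction of the bias depends on why patients stop.

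If the general chi-square were applied to all enrolled patients, rejection would run from about 8% to 36% instead of 5%, depending on AE incidence. This assumes equal constant hazards, medians of 5.9 v 10.5 months, 70 per group and a 24-month cap. A reader might take the upper values, or the roughly 40% reached without a cap, as a property of the plan. They are not: the documents give no SU duration by baseline group, and smaller gaps, rarer AEs or early-onset AEs bring the figure down to about 6-17% or less than 12%, as shown above.

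**What to change.** In Protocol 8.9 and SAP 8.2:
1. Keep the crude frequencies. Beside each, report patient-months at risk, from first SU dose to the earlier of first AE or last dose + 28 days (the window the SAP already uses for deaths), and the exposure-adjusted incidence rate.
2. For any analysis of AEs by baseline factor, use a Cox model for time to first AE, or Poisson regression with a log time-at-risk offset, instead of chi-square on crude frequency.
3. Show cumulative incidence at months 3 and 6, with stopping SU or death as the competing event.
4. Use all patients who received SU as the denominator, and amend the safety population in SAP 4.1, which now contains only patients who had an AE.

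The cost is SAP wording and a few table columns. Treatment changes and AEs are already collected, and Cox models are already in SAP 7.4. AE tables become slightly longer. The rates assume a roughly constant hazard; the cumulative incidence covers AEs that occur early.

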3.2. Rationale and Background

According to the available literature, there is a gap in regards to the real world setting of care and treatment outcome for mRCC, especially in the Middle East and Africa region.

SU has become the standard of care (used as first-line treatment) in many countries as it has the most robust data in the first-line treatment of mRCC. It is also recommended as first line treatment in the NCCN and ESMO guidelines.

In order to understand how care is translated into positive treatment outcomes in the broader mRCC patient population and whether there are differences in outcome associated with various treatment patterns, a prospective observational study is necessary. This study will elucidate for the first time the patterns of care and associated outcomes in Africa Middle East patients with mRCC.

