4.2. Subgroups

4.2.1. Subgroups to meet primary and secondary objectives

- Compare efficacy parameters (PFS, OS) for the combined 1st line SU- 2nd line sequences according to the second line post SU :
 - SU in 1st line-Axitinib TKI in 2nd line
 - SU in 1st line- other TKI in 2nd line (sorafenib, pazopanib)
 - SU in 1st line/mTOR in 2nd line (temsirolimus, everolimus)

CCI [REDACTED]

- [REDACTED]
- [REDACTED]
- [REDACTED]
- [REDACTED]
- [REDACTED]

[figure not shown] 2);

- Incidence of other AEs (grade ≤ 2);
- Incidence of all AE per grade.
- AEs will be analyzed separately for AEs related to SU as solicited and unsolicited AE.
- **Discontinuation due to toxicity**
 - Proportion of patients who discontinued the treatment of interest, because of AEs;
 - Treatment duration until discontinuation for AEs;
- **Deaths**
 - Proportion of patients who died due to any cause, over the treatment period (including the 28 days after the treatment discontinuation) and along the study;
 - Cause of death (tumor-related, other cause).

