5.5. Covariates

- In case of multivariate analyses, baseline characteristics will possibly be used as covariates.
- The final covariates will be selected according to the selection strategy of variables defined in the part 7.6.
- Possible, but not exclusive, baseline covariates related to SU initiation will be limited because of a retrospective part of the data collection, with:
 - Age and sex;
 - ECOG (0, 1, 2, 3, 4), Karnofsky performance status
 - MSKCC risk factors (Favorable, Intermediate, Poor)

- Medical history of hypertension (Yes, No)
- Delay from diagnosis (< 1 year from diagnosis to first metastasis detection/ \geq 1 year)
- Nephrectomy (Yes, No)
- Number of metastatic sites
- The covariates identified previously will be also explored and act as baseline for second line treatment initiation. In this case, other covariates will be:
 - The response to SU treatment in 1st line;
 - Duration of SU treatment, PFS;
 - Previous treatments for primary tumor (surgery, radiotherapy, other);
 - Additional anti-tumor treatments;

6. Handling missing values

- The majority of data will be collected with a website (except for FKSI-19 questionnaires).
- In this website, the input of certain data will be obligatory, limiting the number of missing values, particularly for endpoints.
- Regarding the descriptive analyses of each variable, it will be based on the available data (“observed-case analysis”), considering missing data as non-informative.
- The number of missing data will be documented for each analysis.
- The analysis of the primary endpoint is a survival analysis which is known to efficiently handle missing data: All patients are included in the analysis and missing data are called right-censored data.
- In case of absence of 20% data and over, for a main parameter such as ORR rate, the Hot-deck imputation method could be used. With this method, the missing value is replaced by the observed value of a patient with similar characteristics $X_1, X_2 \dots X_k$. If it does not exist such similar patient, the missing value will be amputated
- A sensitivity analysis will be conducted by the imputation of extreme values. In the one hand, analysis in the most unfavorable situation (i.e. missing data considered as failure) and in the other hand, analysis in the most favorable situation, i.e. missing data considered as success (e.g. for ORR, success is to be responder).

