7.4. Survival analysis methods

- The survival functions for PFS, TTF, TSF, and OS will be estimated with the Kaplan-Meier method. The survival function $S(t)$ is the probability that the event (treatment discontinuation, death or progression) does not occur before a specified time.
- This method will be applied to derive, survival curves, median event time and a 95% confidence interval for the median survival time (time at which half the analyzed patients have presented the event).
- Survival curves will give an idea of whether or not the groups are proportional (i.e. the survival functions are approximately parallel).
- For OS, the share of patients alive at 24 months will also be measured.
- The log-rank test of equality across strata will be used to compare survival curves for categorical variables (sub-groups of interest).
- For continuous variables, a univariate Cox proportional hazard regression will be used.
- For analyses of prognostic factors of survival time, multivariate Cox proportional hazard regressions will be performed.

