7.6. Strategy of selection of variables in multivariate models

- The strategy of selection of variables in multivariate models will be as follows:
 - Identifying baseline patient characteristics significantly associated with survival time in univariate analyses with a p-value of 0.25.
 - All these variables will be included in the model and a backward elimination will be realized (Starting with a complex model and removing terms sequentially until a final model with only explicative variables significantly associated with the survival time, adjusted each other).

8. Statistical Analysis

This chapter presents the planned statistical analyses to meet the study objectives.

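### Efficacy may be compared by events after the first SU dose and is to be compared by second-line type, with time counted from that dose and no visible landmark, time-dependent covariate or reset time origin

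*Protocol*

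**What the plan says.** **Time origin.** Protocol 3.3.3 defines PFS as "the time from when the patient receives the first dose of SU to the time of progression or death". TTF, OS and both combined endpoints start at the same dose (Protocol 3.3.3; SAP Appendix 3).

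**Factors seen after that dose.**
- Protocol 8.9: "Sub-group analyses of association between efficacy outcomes, safety measurements, and baseline factors will be performed for exploratory reasons as needed". It names no method for this.
- SAP 4.2.1: "Compare efficacy parameters (PFS, OS) for the combined 1st line SU- 2nd line sequences according to the second line post SU", split into axitinib, other TKI and mTOR. SAP 8.1.1 repeats the second-line subgroup for combined PFS and OS. Dummy table 9.3 adds a supportive-care column beside the active second-line columns.
- SAP 5.5: "The covariates identified previously will be also explored and act as baseline for second line treatment initiation". It then adds response to SU, SU duration and PFS as further covariates, without giving a new time origin.

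**Methods.** SAP 7.4: "The log-rank test of equality across strata will be used to compare survival curves for categorical variables (sub-groups of interest". It adds univariate and multivariate Cox regression. SAP section 4 sets 5% for all comparisons, with no multiplicity adjustment. No landmark, time-dependent covariate or delayed time origin appears in the visible text.

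**The concern.** To be counted as having had an adverse event, a dose change or a second-line drug, a patient must first remain under observation, and usually event-free, until it happens. If the groups are formed with hindsight but the clock starts at the first SU dose, that waiting time is credited to the group with the later event. Patients who fail early fall into the other group by construction.

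The result is an apparent benefit where none exists. In this study it could read as longer PFS in patients with toxicity or modified dosing, or longer OS in patients who received a second-line drug than in those on supportive care. A hypothesis-generating study would then generate a hypothesis in a predictable wrong direction. The single-arm medians for PFS and TTF are not affected.

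**Working it through.** **The plan's own figure.** None is given for these analyses. The only design figure is the ORR margin: 1.96 × √(0.37 × 0.63 / 140) = 0.080. This reproduces the stated ±8% and supplies N = 140.

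**Inputs from the documents.** N = 140 (Protocol 8.7). Follow-up is to month 24 (8.5.3). Medians of 5.9 and 10.5 months are the first-line SU durations cited in Protocol 6.1.1, used here as stand-ins for PFS or TTF. The same section cites dose reduction or interruption in 50% of patients and places treatment alteration in the first months, without a figure.

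**Assumptions.** Exponential times, uniform 24-month follow-up, median onset of the post-start event from 0.5 to 6 months, and a susceptible share of 50% to 100%. The post-start event has no effect on outcome (true HR 1.0).

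**Method.** 600 simulated studies per scenario, comparing patients who ever had the event with those who never did, from first dose.

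| Outcome median (months) | Susceptible | Median onset (months) | Had event | Apparent HR | Log-rank p<0.05 |
|---|---|---|---|---|---|
| 5.9 | 50% | 0.5 | 46% | 0.86 | 13% |
| 10.5 | 50% | 0.5 | 48% | 0.91 | 8% |
| 5.9 | 60% | 1 | 51% | 0.72 | 49% |
| 10.5 | 60% | 1 | 55% | 0.78 | 27% |
| 5.9 | 70% | 3 | 46% | 0.51 | 98% |
| 10.5 | 70% | 3 | 55% | 0.53 | 90% |
| 5.9 | 100% | 1 | 86% | 0.08 | 100% |
| 10.5 | 100% | 1 | 91% | 0.05 | 100% |
| 5.9 | 100% | 3 | 66% | 0.19 | 100% |
| 10.5 | 100% | 3 | 78% | 0.13 | 100% |
| 5.9 | 100% | 6 | 50% | 0.28 | 100% |
| 10.5 | 100% | 6 | 63% | 0.24 | 100% |

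A separate null simulation with about half of patients affected gave 0.85-0.88, 0.73-0.80 and 0.46-0.49 at onsets of 0.5, 1 and 3 months. With everyone susceptible, extending the onset to 12 months gave 0.37 and 0.34. The very low values arise because, when all are susceptible, the never group consists mostly of patients who failed before their event could occur.

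**Same data, other methods.** A 3-month landmark gave HR 0.98-1.03 with 5%-9% of runs significant. A time-dependent covariate gave 0.98-1.02 with 4%-7%.

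**Cost of the landmark.** Share failing before month 3 = 1 − 0.5^(3/median). For 5.9 months: 1 − 0.703 = 29.7%, or 42 of 140. For 10.5 months: 1 − 0.820 = 18.0%, or 25 of 140.

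**Second-line comparisons.** These were not simulated, because the documents give no share reaching second line and no timing. The structure can still be read off. Patients on any active second-line drug have all survived to start it, so guaranteed time is partly shared among those groups. Supportive-care patients need not have survived to any such start. Further, combined TTF = SU duration + any gap + second-line duration. Using SU duration as a covariate for it, with time from first dose, relates a total to one of its own parts.

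**The case against.** A reader might infer that the plan applies log-rank and Cox tests to adverse-event or dose-change groups, and that large false benefits will follow. The documents do not support that.

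- Protocol 8.9 names no method for the safety associations and makes them optional. The sentence can even be read as efficacy and safety each examined by baseline factors.
- Its Cox sentence is confined to baseline factors: "Cox proportional hazard models may be used to explore the potential influences of baseline characteristics on PFS or TTF". So is variable selection in SAP 7.6: "Identifying baseline patient characteristics significantly associated with survival time in univariate analyses with a p-value of 0.25".
- Protocol 3.2 asks "whether there are differences in outcome associated with various treatment patterns", but as rationale. The objectives only describe SU dosing.
- SAP 8.2 treats safety descriptively, and no visible dummy table crosses efficacy with adverse events or dose changes.
- SAP text after 4.2.1, in part of chapter 5 and after 8.3 is redacted or not shown. An analysis or a safeguard there can be neither ruled in nor ruled out.
- Protocol 8.11 limits the study to hypothesis generation.

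All of this stands against saying that the plan will produce large bias. It does not remove the gap. An analyst who carries out Protocol 8.9 on a survival endpoint finds only first-dose methods in SAP 7.4. The comparison by second-line type is written into the SAP, not optional. An exploratory label does not correct a bias whose direction is known beforehand.

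Hazard ratios near 0.1-0.4 should not be taken as the expected size either. They need every patient to be susceptible. With about half affected and very early onset, the distortion is modest.

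**Conclusion.** The point holds as a risk that the visible plan leaves open. Efficacy may be related to post-start safety events, and is to be compared by second-line type, from the first SU dose and without a stated method that respects when those factors become known.

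The bias runs towards false benefit. With about half of patients affected, and up to 70% susceptible, the apparent HR is roughly 0.85-0.91 for a median onset of 0.5 months, 0.72-0.80 for 1 month and 0.46-0.53 for 3 months. With all patients susceptible and onset medians of 1 to 12 months it is 0.05-0.37. These figures rest on assumed onset times, exponential times and uniform follow-up; the documents quantify none of the onset times.

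For second-line type no size can be given. The concern is sharpest against supportive care and weaker among active drugs.

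**What to change.** Add to SAP 7.4 and Protocol 8.9:

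- **(a)** Any factor first observed after the first SU dose (adverse event, dose or schedule change, interruption) is related to PFS, TTF or OS only as a time-dependent covariate or by a landmark analysis. An example is month 3, the first scheduled follow-up visit. Patients still event-free and in follow-up at the landmark are grouped by status then, and time runs from there. Ordinary log-rank and Cox from first dose are kept for factors known at first dose.
- **(b)** Comparisons by second-line type, and models using response to SU or SU duration as covariates, count time from second-line start among patients who start second-line therapy. Combined endpoints from first dose, and the supportive-care column of table 9.3, are reported descriptively without tests.

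A 3-month landmark alone would not serve for (b), because second-line treatment will often start later. Set the landmark by date from first dose, since visits may deviate by 6 weeks.

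**Cost.** A few sentences, with no extra visits or patients. The landmark excludes those who progress, die or leave follow-up before month 3: about 18%-30% under the two medians from failure alone. Part (b) gives up formal tests on the combined endpoints. Both parts need dates for adverse events, dose changes and second-line start. The visible text does not list these dates, and Protocol 8.5 lets uncollected items stay blank, so the eCRF should be checked. Neither method removes confounding.
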